**Table 1 Study Products**

Product	Flavor	Nicotine Strength	Figure and Table Code
A	[REDACTED]	2.4%	A
B	[REDACTED]	2.4%	B
C	[REDACTED]	2.4%	C
D	[REDACTED]	2.4%	D
E	[REDACTED]	2.4%	E
F	Subject's Usual Brand Combustible Cigarette		F

Statistical Analysis Plan  
Protocol No.: Fontem-PK-01

## **4. RANDOMIZATION AND BLINDING**

### **4.1. RANDOMIZATION**

Eligible subjects at Visit 2 will be assigned a randomization number beginning with 2001. The randomization will determine the order in which the subjects will test the study products at Visits 3 to 7. The randomization code for the study products will be produced using a computer-generated Latin-square procedure.

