5.2 Replacement of Subjects

The study aims to have 20 subjects complete all 6 study visits (Visits 2-7). Twenty of the subjects who have qualified at Screening will be scheduled to attend Visit 2. An additional 2 qualified subjects will be designated as alternates. They will also attend Visit 2 but will only be randomized if any of the original 20 subjects do not complete Visit 2. After Visit 2, subjects who drop out or are withdrawn may be replaced at the discretion of sponsor.

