All blu disposable e-cigarettes (Table 1) will be provided by the sponsor. At Visit 2, subjects will smoke their own brand of combustible cigarette.

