### **7.3. DATA HANDLING RULES**

#### **7.3.1. Missing Data**

Missing data will not be imputed. Where individual data points are missing because of dropouts or other reasons, the data will be considered missing at random and summarized based on reduced denominators.

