## 8.9. PHARMACOKINETIC ANALYSIS OF NICOTINE PLASMA CONCENTRATION

PK parameters of plasma nicotine levels will be calculated using noncompartmental methods with the Phoenix WinNonlin version 8.3 software platform (Certara, Princeton, NJ). Plasma concentrations and the computed plasma PK parameters will be listed for each study product and subject.

The following PK parameters will be calculated; all parameters will be baseline-adjusted using the value at time -5 minutes:

- $C_{max,0-120}$  = Maximum plasma concentration during defined use session
- $T_{max,0-120}$  = Time of maximum plasma concentration during defined use session
- $AUC_{0-120}$  = Area under the plasma concentration-time curve from time 0 to 120 minutes during defined use session
- $C_{avg,0-120}$  = Average concentration from 0 to 120 minutes defined as  $AUC_{0-120}/120$  minutes
- $C_{max,120-180}$  = Maximum plasma concentration during the *ad libitum* puffing session
- $T_{max,120-180}$  = Time of maximum plasma concentration during the *ad libitum* puffing session
- $AUC_{120-180}$  = Area under the plasma concentration-time curve from time 120 minutes to 180 minutes during the *ad libitum* puffing session
- $C_{avg,120-180}$  = Average concentration from 120 to 180 minutes defined as  $AUC_{120-180}/60$  minutes
- $AUC_{0-180}$  = Area under the plasma concentration-time curve from time 0 minutes to 180 minutes during both puffing sessions
- $RC_{max}$  = Ratio of  $C_{max,120-180}/C_{max,0-120}$
- $RC_{avg}$  = Ratio of  $C_{avg,120-180}/C_{avg,0-120}$

A one-way or repeated measures analysis of variance will be conducted on the Outcomes Population  $C_{max,0-120}$  and  $AUC_{0-120}$  to assess for statistical differences between the Usual Brand combustible cigarette and the blu disposable e-cigarettes. Significance based on a Dunnett's multiple comparison assessment will be reported.

Statistical Analysis Plan  
Protocol No.: Fontem-PK-01

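### The planned ANOVA names no visit term although the order of A-E over Visits 3-7 is set by Latin square, so visit drift stays in the error and, if the squares break, enters the product means

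*SAP*

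**What the plan says.** SAP 4.1 fixes what is randomised: "The randomization will determine the order in which the subjects will test the study products at Visits 3 to 7". It also gives the method: "The randomization code for the study products will be produced using a computer-generated Latin-square procedure". The size and replication of the square are not stated. The comparator lies outside the randomisation (SAP 3.4): "At Visit 2, subjects will smoke their own brand of combustible cigarette".

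The only inferential analysis is in SAP 8.9: "A one-way or repeated measures analysis of variance will be conducted on the Outcomes Population", applied to Cmax,0-120 and AUC0-120, "to assess for statistical differences between the Usual Brand combustible cigarette and the blu disposable e-cigarettes". Then: "Significance based on a Dunnett's multiple comparison assessment will be reported". No model terms are listed, the choice between the two ANOVAs is left open, and no contrast among A-E is planned. SAP 8.11 puts the randomisation data in listings only.

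Two other provisions affect balance. For missing values, SAP 7.3.1 says "the data will be considered missing at random and summarized based on reduced denominators". On replacement, Protocol 5.2 says "After Visit 2, subjects who drop out or are withdrawn may be replaced at the discretion of sponsor", with no rule for which sequence a replacement receives.

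**The concern.** A Latin square spreads each product evenly over the visits so that a visit effect can be separated from the product effect. Neither ANOVA named in SAP 8.9 carries a visit term as it stands, so any systematic change over Visits 3-7 is treated as noise. Under the one-way option, differences between subjects are treated as noise too.

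Some drift is plausible on the protocol's own terms. Subjects are smokers who need be no more than occasional e-cigarette users (4.1.1). The defined session sets the number and spacing of puffs but only a minimum puff duration of 1 second (9.14.1). Technique, and with it nicotine uptake, could change over five e-cigarette visits.

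At stake is the precision of every planned contrast. Once the squares are incomplete, the product means can also pick up part of the visit effect.

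**Working it through.** The plan has no figure to reproduce: SAP 6 justifies 20 subjects by precedent, without a power calculation.

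**Inputs from the documents.** 20 subjects; cigarette at Visit 2; A-E over Visits 3-7.

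**Assumptions.** Four replicates of a 5x5 square, all subjects complete, analysis on the log scale, linear drift of *d* log units per visit, within-subject CV 30-40%.

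**1. Drift left in the error (repeated measures option).** Visits 3-7 have centred positions -2 to 2, with squares summing to 10. In complete squares, visit is orthogonal to product and subject, so its whole sum of squares, 20 x 10 x *d*², falls into the residual. Residual df = 120 - 1 - 19 - 5 = 95. The added error variance is 200*d*²/95.

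Within-subject log variance is ln(1 + CV²): 0.0862 (SD 0.294) at 30% and 0.1484 (SD 0.385) at 40%.

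| *d* | Added variance | SD at CV 30% | SD at CV 40% |
|---|---|---|---|
| 0.05 | 0.0053 | 0.302 (+3.0%) | 0.392 (+1.8%) |
| 0.10 | 0.0211 | 0.327 (+11.5%) | 0.412 (+6.9%) |

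Standard errors scale with the residual SD. At *d* = 0.10, precision is that of 20/1.115² = 16.1 or 20/1.069² = 17.5 subjects. Reading 10% as ln(1.10) = 0.0953 instead gives +10.5% and +6.2%.

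**2. One-way option.** With within-subject correlation ρ, error variance is 1/(1 - ρ) times the within-subject variance: 1.4, 2.0 and 3.3 at assumed ρ of 0.3, 0.5 and 0.7. This can far exceed the visit effect.

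**3. Broken squares.** As an illustration, suppose two of one product's four Visit 7 sessions are lost. The mean position of its remaining 18 sessions is -4/18 = -0.22 visit, so at *d* = 0.10 its mean shifts by about 2%.

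**4. What a visit term can estimate.** A six-level visit factor added to subject and product gives 30 columns of rank 29. A-E contrasts are estimable, but cigarette contrasts are not, because Visit 2 and the cigarette are the same indicator. Coding visit to sum to zero within Visits 3-7 adds four columns, leaves 91 df and keeps the cigarette contrasts estimable.

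**5. Effect on the Dunnett test.** With drift confined to Visits 3-7 and centred, simulated familywise error without a visit term was 4.0%, 3.6% and 1.2% at drifts of 0.1, 0.25 and 0.5 within-subject SD per visit. It was about 5% with no drift, so the omission makes the test conservative. If drift also runs from Visit 2, each e-cigarette contrast is biased by three visits' drift (mean visit 5 minus 2), with or without the term.

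**The case against.** The documents supply no drift, CV or missing-visit rate, and at 5% per visit the loss is only 2-3%. The design also limits learning in the tested parameters: ten puffs at fixed spacing, a trial use at screening (Protocol 9.13) and a day of home familiarisation before each e-cigarette visit (4.3.4). Protocol 5.2 aims for 20 completers. All of this stands, and it makes the point a moderate one.

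The fix also does little for the planned comparison if drift starts at Visit 2. In one simulation at 0.25 SD per visit, familywise error was 72% without the term and 78% with it, because the narrower standard error makes a biased contrast slightly easier to declare significant. That stands too, and the confounding has to be stated openly.

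It can be said that SAP 8.9 is a summary and that a visit term is not excluded. But Protocol 10 defers detailed methods to the SAP, and SAP 2 says it provides them and supersedes the protocol. SAP 8.9 nevertheless repeats the protocol's sentence without adding a model.

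Three stronger readings are tempting but not supported:

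- A reader might infer that the randomisation is never used. Complete squares still balance order across products without a visit term: the simulated bias in any A-E mean relative to the others was under 0.01 SD. Only the model ignores the order.
- A reader might infer that comparing flavours with each other belongs to the first objective. SAP 3.2.1 sets the e-cigarettes against the combustible cigarette, which is what Dunnett addresses.
- A reader might infer that one missing visit removes a subject, losing 17-26% of subjects if 3-5% of visits fail (1 - 0.97⁶, 1 - 0.95⁶). That holds only for a complete-case routine, and the SAP names none.

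**Conclusion.** The point holds in moderate form. The SAP balances a factor by design and then names no term for it in its only test. The cost is lost precision while the squares are complete, plus some contamination of the product means if they are not. The size depends on the assumed linear drift and CV: negligible to small at 5% per visit, and the equivalent of losing about 2.5 to 4 of 20 subjects at 10%. Leaving the one-way option open could cost more than omitting visit.

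The missing-at-random statement in SAP 7.3.1 is also poorly served by reduced-denominator means, which adjust for neither subject nor visit. The absence of A-E contrasts is a missed use of the only randomised comparison, not a failed objective. The cigarette's confounding with Visit 2 is a separate limitation that no choice of model removes.

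**What to change.** In SAP 8.9 and the matching text in the protocol synopsis and Protocol 10.3.1, replace the choice of ANOVAs with one linear mixed model:

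- all available visits in the Outcomes Population;
- random subject and fixed product;
- fixed visit within Visits 3-7, coded to sum to zero, with no visit effect for the cigarette session;
- Dunnett comparisons of each e-cigarette with the usual brand, as now.

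A-E estimates with 95% confidence intervals may be reported from the same model, labelled descriptive. State that every cigarette contrast remains fully confounded with Visit 2 and that the model does not correct this.

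The cost is 4 residual degrees of freedom against the repeated measures option (95 to 91); the one-way option starts from 114. No new data are needed. Protocol 10 requires an amendment for major changes to the analysis of primary endpoints, so the sponsor should decide whether this qualifies and, if the protocol text is left as it is, record the change in SAP 9.

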### **4.2. BLINDING**

It is not possible to blind the study products.

## **5. DEFINITION OF ANALYSIS POPULATIONS**

### **5.1. Safety Population**

The Safety Population will include all subjects who have successfully completed eligibility requirements and using at least one study product.

The Safety Population will be used to summarize subject disposition, demographics and baseline characteristics, and safety data.

### **5.2. Outcomes Population**

The Outcomes Population is a subset of the Safety Population and will consist of subjects who use a study product and have evaluable PK, subjective effects, or topography data.

The Outcomes Population will be used in the summary and analysis of PK, subjective effects, topography, and product use.

### **5.3. Pharmacokinetic Subpopulation**

The PK Subpopulation is a subset of the Outcomes Population and will consist of subjects who appear to have met the pre-exposure smoking abstinence period (Section 8.9.2).

The PK Subpopulation will be used in the summary of PK parameters.

## **6. SAMPLE SIZE CALCULATION**

Since this study is the first to examine the nicotine PK in subjects using these blu disposable e-cigarettes, no formal power calculations were performed. The sample size is typical of other studies reported in literature examining the PK and subjective effects of different tobacco/nicotine products. A sample size of 20 subjects has been determined adequate to meet the study objectives.

Statistical Analysis Plan  
Protocol No.: Fontem-PK-01

## **7. GENERAL STATISTICAL CONSIDERATIONS AND DEFINITIONS**

### **7.1. BASELINE AND VISIT WINDOWS**

Unless otherwise specified in this section, baseline, which is defined as the last non-missing assessment prior to the first product use within a visit, will be used in baseline and change from baseline analyses. Baseline adjustment will be performed by subtraction of the baseline nicotine concentration from each nicotine concentration obtained after test product use on that day for each subject.

The summary tables by visit will use the values from the scheduled visit.

### **7.2. SUMMARY STATISTICS**

Continuous variables will be summarized using descriptive statistics including number of subjects, mean, median, standard deviation (SD), minimum and maximum values of the raw data, coefficient of variance (CV; PK concentration and PK parameters), geometric mean, and geometric CV (%) (PK parameters only). Means and medians will be reported to one more significant digit than the raw data values being analyzed. Standard deviations will be reported to two more significant digits, and the minimum and maximum will be reported to the same number of significant digits as the raw data values being analyzed.

Categorical variables will be summarized as the number and percentage of subjects per category. All percentages will be rounded to one decimal point. To ensure completeness, all summaries for categorical and discrete variables will include all categories, even if none of the subjects had a response in a particular category. Denominators for each analysis will be based on the population of interest (e.g., Safety Population; subjects with non-missing data) unless otherwise noted.

In general, all data will be listed by subject and time point.

SAS software (version 9.3 or higher, Cary, NC) will be used for data presentation and summarization including summary tables, graphs, and data listings not associated with the nicotine concentration or PK parameters.

### **7.3. DATA HANDLING RULES**

#### **7.3.1. Missing Data**

Missing data will not be imputed. Where individual data points are missing because of dropouts or other reasons, the data will be considered missing at random and summarized based on reduced denominators.

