### **3.4. STUDY DESIGN**

This will be a part-randomized, open-label abuse liability assessment and puffing topography study of nicotine-containing products carried out in 20 healthy adult volunteers who smoke combustible cigarettes. The schedule of events is presented in Section 10.

Statistical Analysis Plan  
Protocol No.: Fontem-PK-01

After screening, subjects will attend the study site 6 times (Visits 2-7). Prior to each visit, subjects will be required to refrain from using any nicotine-containing products for a period of at least 12 hours before study product use.

During their second visit (Visit 2), the subjects will smoke their usual brand cigarette during 2 use sessions. In the first session, subjects will smoke a single combustible cigarette of their usual brand by taking 10 puffs, 30 seconds apart. Blood samples (5 mL) will be obtained for plasma nicotine analysis at -5, 3, 5, 7, 10, 15, 20, 30, 45, 60, 90, and 120 minutes relative to the first puff on the cigarette. Blood pressure and heart rate will be recorded at -10 (baseline), 8, 60, and 120 minutes. Subjects will be asked to complete several subjective effects questionnaires at various points either before, during, or after product use.

In the second session, which will begin immediately after the 120 minute blood draw and after all questionnaires have been completed, subjects will be allowed to take *ad libitum* puffs on their usual brand cigarette for a period of 60 minutes (1 hour) while puffing topography measurements are made with a CReSS Pocket device. Subjects may use as many cigarettes as they like. Blood samples for nicotine PK analysis will be drawn at 135, 150, 165, and 180 minutes relative to the first puff on the cigarette at the visit (i.e., at 15, 30, 45, and 60 minutes of the *ad lib* session). Blood pressure and heart rate will be recorded at 180 minutes. Subjective effects questionnaires will also be completed at specified time points.

At the end of Visit 2, subjects will be randomized into a product use sequence for testing the investigational products (blu disposable e-cigarettes).

Subjects will then visit the study site on 5 subsequent occasions (Visits 3-7); at each visit, the subjects will use their assigned blu disposable e-cigarette during 2 use sessions (standardized and *ad lib*, same as at Visit 2). Study procedures during the 2 use sessions will be the same as at Visit 2.

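### A missing-at-random assumption does not justify reduced-denominator means, and drop-out falls mainly on the e-cigarette visits: a modest bias of unknown direction

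*SAP*

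**What the plan says.** SAP 7.3.1 does not impute. It covers values lost through drop-out or from any other cause, and its rule for them is that "the data will be considered missing at random and summarized based on reduced denominators". Protocol 10.3 has the same rule.

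The order of use is fixed for the cigarette and randomized for the rest. SAP 3.4: "At Visit 2, subjects will smoke their own brand of combustible cigarette", and "At the end of Visit 2, subjects will be randomized into a product use sequence for testing the investigational products". SAP 4.1: "The randomization code for the study products will be produced using a computer-generated Latin-square procedure". The five e-cigarettes therefore occupy Visits 3 to 7.

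Protocol 5.2 names two alternates to cover losses at Visit 2, on these terms: "They will also attend Visit 2 but will only be randomized if any of the original 20 subjects do not complete Visit 2". For losses later in the study, the same section leaves replacement open: "subjects who drop out or are withdrawn may be replaced at the discretion of sponsor".

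On analysis, SAP 8.9 states: "A one-way or repeated measures analysis of variance will be conducted on the Outcomes Population". This covers Cmax0-120 and AUC0-120 only, with Dunnett comparisons against the cigarette. SAP 5.2 admits to that population anyone who uses a study product and has some evaluable data, so complete visits are not required. No rule says how a subject with a missing visit enters the ANOVA. Product liking, intent to use and PES are primary endpoints (SAP 3.3.1), but Protocol 10.3.2 and SAP 8.7 plan no model for them. No missing-data sensitivity analysis is planned.

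**The concern.** The stated assumption and the stated method do not match. Missing at random allows drop-out to depend on what has already been observed, for example leaving after scoring an e-cigarette poorly. A raw mean over the subjects still present is then a mean over a selected group. It is unbiased in general only when missingness has nothing to do with the outcome.

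The fixed first position of the cigarette makes the loss lopsided. A subject who leaves between Visits 3 and 7 keeps a cigarette value and loses e-cigarette values. The Latin square spreads that loss over products A to E but does not balance it against the cigarette. The comparison with the cigarette is the primary PK objective. For liking, intent to use and PES, the reduced-denominator summaries are the whole planned result.

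**Working it through.** The plan gives no drop-out rate, SD or effect size, so there is no figure of its own to reproduce. Everything numeric below except the 20 subjects and the visit order is an assumption.

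**Principle.** With R = 1 when a value is observed, the bias of an available-case mean is approximately Cov(R, Y) / P(R = 1). It is zero when R is unrelated to Y and generally not zero under missing at random.

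**Illustration on a liking score.** Assumed: 100-point scale, true e-cigarette mean 45, between-subject SD 20, within-subject SD 12, and a 25% or 50% chance of leaving after a score below 20.

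- Variance: 20² + 12² = 544, so the SD is 23.3. Within-subject correlation: 400/544 = 0.735.
- Average score of those below 20: z = (20 − 45)/23.3 = −1.07, giving 45 − 23.3 × 0.2246/0.1419 ≈ 8.1, which is 36.9 below the mean.
- Their expected later scores lie 0.735 × 36.9 = 27.1 points below the mean.
- With 2.3 subjects gone by Visit 7, that visit's mean rises by 2.3 × 27.1/17.7 = 3.5 points. With 3.8 gone, it rises by 3.8 × 27.1/16.2 = 6.4.
- Losses build up from none at Visit 3. Averaging over Visits 3 to 7 roughly halves these figures, to about 1.8 and 3.2.

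Simulation (4,000 trials per setting; ranges cover repeat runs; cigarette mean assumed 75 with the same subject effect) agrees:

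| Bias in points, low scorers leave | 25% chance | 50% chance |
|---|---|---|
| Incomplete subjects of 20 | 2.3 | 3.8 |
| Available-case e-cigarette mean | +1.6 to +1.8 | +3.0 to +3.1 |
| Listwise e-cigarette mean | +3.6 | +6.1 to +6.2 |
| Listwise cigarette mean | +3.3 | +5.7 |
| Listwise contrast | +0.2 | +0.4 |
| Random-subject model | 0.0 | 0.0 |

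If leaving is triggered instead by scores above 70, the available-case bias becomes about −1.6 to −1.8 and −3.1.

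**Wider range.** A second simulation (8,000 trials per scenario, outcome SD 1, true difference 0) used 10 to 30% total drop-out, within-subject correlation 0.3 to 0.7, and log-odds slopes of −1 or +1 per SD. Bias in the available-case difference between e-cigarette and cigarette, in SD:

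- Drop-out unrelated to outcome: at most about 0.005.
- Drop-out driven by the previous e-cigarette response: about 0.01 to 0.08, either sign (0.04 at 20% drop-out and correlation 0.5).
- Cigarette response also driving drop-out: up to about 0.13.
- Drop-out driven by the subject's own underlying level, which is not missing at random: up to about 0.15.

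In all of these the available-case cigarette mean stays within 0.01 of the truth, because this simulation puts all drop-out after Visit 2. A random-intercept model in one large sample (6,000 subjects, correlation 0.5, 23% drop-out) gave +0.01 and −0.01, where the available-case differences were +0.08 and −0.06.

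**Scale.** In the liking example the standard error of one product mean is 23.3/√20 = 5.2. That of a within-subject contrast between two products is √(2 × 144/20) = 3.8.

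**The case against.** The strongest reply is that this is a 20-subject Phase I study with no power calculation, and its subjective measures are descriptive by design. The number of subjects accompanies every continuous summary and data are listed by subject (SAP 7.2). Discontinuations and their reasons are tabulated (SAP 8.1). A bias of 1.6 to 3.1 points lies inside one standard error of a product mean, and it comes from invented inputs. The mixed model's zero bias is partly built in, since the data were generated from that model. All of this stands, and it limits the point to a modest one. It does not make the stated method valid under the stated assumption.

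A reader might infer four stronger things that the documents do not support.

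- *All drop-out follows the cigarette visit.* Protocol 5.2 foresees subjects not completing Visit 2, and SAP 7.3.1 covers losses for other reasons, which can occur at any visit.
- *Only the e-cigarette results are distorted.* That holds for raw means with drop-out after Visit 2. If the ANOVA deletes incomplete subjects, the cigarette mean moves as well.
- *The bias favours the e-cigarettes.* Protocol 5.1 lists withdrawal of consent, noncompliance, adverse events and investigator decision, with no direction implied, and the sign reverses if high scorers leave. In an abuse liability assessment, higher liking or uptake is not plainly favourable either.
- *A repeated-measures ANOVA that deletes incomplete subjects makes the comparison worse.* It shifts each product mean more, but most of the shift cancels in the contrast (0.2 to 0.4 points here). Its main cost is lost data. Nor does the SAP say that it deletes anyone: a likelihood-based repeated-measures model would already be valid under missing at random.

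**Conclusion.** The point holds in limited form. Reduced-denominator means do not follow from a missing-at-random assumption. With the cigarette fixed at Visit 2, drop-out mainly thins the e-cigarette data, so the two sides of the comparison can rest on different subjects. Replacing drop-outs adds subjects but does not undo the selection.

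The direction is unknown and the size is modest: about 1.6 to 3.1 points of 100, either sign, with 2 to 4 of 20 subjects incomplete. The upper figure is about 0.8 of the standard error of a two-product contrast (3.1/3.8). These sizes rest on the assumed means, SDs and leaving rules; with little drop-out the problem nearly vanishes.

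The mixed model is valid if drop-out depends only on observed values of the outcome being modelled. Losses driven by something else are not fully covered. Even so, when drop-out was driven by the subject's underlying level, the within-subject difference stayed near zero in the simulation.

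**What to change.** - **SAP 8.9:** replace the choice between one-way and repeated-measures ANOVA with one linear mixed model (product fixed, subject random) for Cmax0-120 and AUC0-120. Fit it to all observed visits in the Outcomes Population, with Dunnett-adjusted contrasts of A to E against the cigarette. State that subjects with a missing visit are not deleted.
- **SAP 8.7:** add the same model-based e-cigarette-minus-cigarette contrasts for liking, intent to use and PES, beside the planned raw descriptives with n per product.
- **SAP 7.3.1:** say that the missing-at-random assumption supports the model-based contrasts, and that reduced-denominator summaries are descriptive.

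The cost is SAP wording, an entry in SAP section 9 and a little more analysis; no new data are needed. The downside is that model-based estimates appear beside raw means and will differ slightly from them when visits are missing. Protocol section 10 requires an amendment for major changes to the analysis of primary endpoints, so the sponsor should record whether this counts as one.
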